#### **12.1.2 Safety variables**

A treatment-associated adverse event (TAAE) is defined as an AE that was not present at baseline, or an exacerbation of a pre-existing AE. For laboratory data, a treatment-associated abnormal laboratory value (TAAV) represents an abnormal value that was normal at baseline.

Safety variables of analysis include the following:

- Proportions of patients with any TAAEs
- Proportions of patients with serious TAAEs
- Proportions of patients with Grade 3 or greater TAAEs
- Proportions of patients with severe TAAE
- Proportions of patients with TAAEs leading to study drug discontinuation
- Proportions of patients with TAAEs leading to dose modifications
- Proportions of patients with drug-related TAAEs
- Proportions of patients with TAAVs
- Mean and median changes from baseline in vital signs
- Mean and median changes from baseline in clinical laboratory measures
- Mean and median changes from baseline in measures from electrocardiography.

It is noted that patients who cross over from placebo to receive open-label regorafenib will have treatment-related derivations from first dose of placebo during the double-blind period and treatment-related derivations from first dose of regorafenib during the open-label portion of the study.

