#### **2.4.3 Pediatric tumors: phase I clinical trial and RP2D determination**

Regorafenib was evaluated as a single agent in a multicenter, open-label, non-randomized, phase I dose-escalating study designed to define the safety profile, MTD, RP2D, PK, pharmacodynamics, preliminary tumor response, and acceptability/palatability of the formulations (tablets and granulates) in pediatric subjects with solid malignant tumors which are recurrent or refractory to standard therapy. Data from this trial is described below (all information were taken from the study interim report, dated 19 August 2016).

A total of 55 pediatric subjects with advanced, histologically or cytological confirmed solid malignant tumors were enrolled at 4 different regorafenib dose levels. Forty-one subjects who received at least 1 dose of regorafenib were valid for the safety and PK analyses, 23 subjects were valid and included in the analysis of MTD, and 39 subjects were valid for the efficacy analysis. The median age of subjects was 13.0 years (range: 3 to 17 years of age).

**Safety:** Regorafenib was tolerable at doses up to 82 mg/m^2 in pediatric patients, and safety was consistent with the known safety profile of regorafenib in the adult population. All 41 treated subjects had at least 1 TEAE.

The most frequent TEAEs ( $\geq 10\%$  of 41 treated subjects) were: vomiting (51.2%), pyrexia (48.8%), headache (43.9%), AST increased, fatigue and nausea (41.5% each), ALT increased (39.0%), palmar-plantar erythrodysesthesia syndrome (HFSR) and blood bilirubin increased (31.7% each). (MedDRA preferred terms). The most common TEAEs of Grade 3 or above (Grades 3/4/5), irrespective of relationship to study drug, occurring in more than 5% of all 41 treated subjects were death (12.2%), headache (9.8%), lymphopenia, neutropenia, thrombocytopenia, vomiting, ALT increased, hydrocephalus, dyspnoea, and rash maculopapular (7.3% each).

In total, 40 of all 41 treated subjects (97.6%) reported at least 1 regorafenib related TEAE and the majority were Grade 2 (22 subjects, 53.7%). Drug-related TEAEs occurring in  $\geq 20\%$  subjects in the safety analysis set were AST increased (34.1%), nausea, fatigue, ALT increased, blood bilirubin increased, and palmar-plantar erythrodysesthesia syndrome (HFSR) (31.7% each), pyrexia (29.3%), decreased appetite (26.8%), neutropenia, and thrombocytopenia (24.4% each).

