**Table 6.3.2 Recommended dose modification for hand-foot-skin reactiona**

Grade of event (NCI-CTCAE v 4.03)	Occurrence	Suggested Dose Modification
Grade (G) 1	Any	Maintain dose level and immediately institute supportive measures for symptomatic relief
G 2	1 st occurrence	Consider decreasing dose by one dose level and immediately institute supportive measures. If no improvement, interrupt therapy for a minimum of 7 days, until toxicity resolves to G 0-1 b, c
	No improvement within 7 days or 2 nd occurrence	Interrupt therapy until toxicity resolves to G 0-1. c When resuming treatment, decrease dose by one dose level b
	3 rd occurrence	Interrupt therapy until toxicity resolves to G 0-1. c When resuming treatment, decrease dose by one dose level. b, d
	4 th occurrence	Discontinue therapy
G 3	1 st occurrence	Institute supportive measures immediately. Interrupt therapy for a minimum of 7 days until toxicity resolves to G 0-1. c When resuming treatment, decrease dose by one dose level. b, d
	2 nd occurrence	Institute supportive measures immediately. Interrupt therapy for a minimum of 7 days until toxicity resolves to G 0-1. c When resuming treatment, decrease dose by one additional dose level b, d
	3 rd occurrence	Discontinue treatment permanently.

a. More conservative management is allowed if judged medically appropriate by the investigator.
 
b. If toxicity returns to G 0-1 after dose reduction, dose re-escalation is permitted at the discretion of the investigator if subject has completed one cycle at reduced dose without recurrence of event.
 
c. If there is no recovery after a 4 week delay, treatment with regorafenib or placebo will be discontinued permanently.
 
d. Subjects requiring > 2 dose reductions should go off protocol therapy.
 
e. The maximum daily dose is 160 mg
		

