## **7. ADVERSE EVENTS: LIST AND REPORTING REQUIREMENTS**

Adverse event (AE) monitoring and reporting is a routine part of every clinical trial. The following list of AEs (Section 7.1) and the characteristics of an observed AE (Section 7.2) will determine whether the event requires expedited reporting **in addition** to routine reporting. For routine reporting it is expected that all adverse events grade 3 or greater are recorded.

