### **7.2 Handling of Safety Parameters**

#### **7.2.1 Reporting of Adverse Events**

**All adverse events (related and unrelated) Grade 3 or worse** occurring during the study and up to 30 days after the last dose of study medication must be reported. Reporting the specific time of onset of a given AE is only necessary when it occurs in relation to study drug administration.

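### Section 12.1.2 plans all-grade adverse-event proportions and an ECG change, but the protocol sets no explicit duty to record non-serious Grade 1–2 clinical events and schedules ECG only before treatment

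*Combined protocol and SAP*

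**What the plan says.** Section 12.1.2 defines a treatment-associated adverse event (TAAE) without a severity threshold: it is "defined as an AE that was not present at baseline, or an exacerbation of a pre-existing AE". The listed variables include "Proportions of patients with any TAAEs", drug-related TAAEs, TAAEs leading to dose modification and TAAEs leading to discontinuation of study drug. A separate line reads "Proportions of patients with Grade 3 or greater TAAEs", so the unqualified variables must cover all grades. The list also has "Mean and median changes from baseline in measures from electrocardiography".

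The collection rules are set elsewhere. Section 7 states: "For routine reporting it is expected that all adverse events grade 3 or greater are recorded". Section 7.1.1.3 asks for detailed eCRF reporting from Grade 3 upward. Section 7.2.1 requires reporting of "All adverse events (related and unrelated) Grade 3 or worse" up to 30 days after the last dose.

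Three provisions reach below Grade 3:
- Section 7.1.3 puts clinically significant laboratory abnormalities on the AE eCRF, including those that change study medication.
- Section 7.2.2 requires serious adverse events to be reported.
- Section 11.1.3 requires immediate notification of listed special-interest events, some with no grade limit.

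ECG appears in the screening list (Section 9.1) and has one mark in the study calendar (Section 9.4), in the pre-study column.

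**The concern.** The analysis section asks for more than the collection sections require. A table headed *any TAAE* whose mandatory content is mostly Grade 3 or worse would be read as an all-grade table. Where some sites enter lower grades voluntarily and others do not, the proportion partly reflects site habit.

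The dose-modification and discontinuation variables are exposed in a particular way. The protocol lets Grade 2 clinical toxicity change dosing, so some of the events these variables are meant to count fall in the gap. The laboratory rule adds an asymmetry: a laboratory cause of a dose change counts at any grade, while a non-serious clinical cause must be recorded only from Grade 3.

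Adverse-event incidence is a secondary objective in all five cohorts (Section 1.2). The ECG summary is a separate mismatch: a change needs a second measurement, and none is planned.

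**Working it through.** The documents give no figure to reproduce, so the check compares what each variable needs with what must be collected, then sizes the gap from the protocol's own data.

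**1. Variables against collection duties**

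| Variable in 12.1.2 | Needs | Required by the text | Result |
|---|---|---|---|
| Any TAAE | All grades | Grade 3+, SAEs, significant laboratory findings, special-interest events | Gap: non-serious Grade 1–2 clinical events |
| Drug-related TAAE | All grades | Same | Same gap |
| Leading to dose modification | Any grade that changes dosing | Same; laboratory causes covered by 7.1.3 | Gap for clinical causes below Grade 3 |
| Leading to discontinuation | Any grade that stops drug | Same | Same gap |
| Serious; Grade 3 or greater | Serious or Grade 3+ | Covered | No gap |
| Laboratory and vital-sign change | Repeated measures | Scheduled at visits | No gap |
| ECG change | Baseline and later ECG | Pre-study ECG only | No planned value |

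**2. Can events in the gap change dosing?** Yes, in several places.
- Section 6.1 allows clinically significant Grade 2 toxicity to qualify for delay or reduction.
- For a first Grade 2 hand-foot skin reaction, Table 6.3.2 says "Consider decreasing dose by one dose level and immediately institute supportive measures". Later Grade 2 occurrences lead to interruption and, at the fourth, to discontinuation.
- Table 6.4.1 holds study drug for symptomatic Grade 2 hypertension.

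None of these is a laboratory abnormality, so Section 7.1.3 does not bring them onto the eCRF.

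**3. Size, from the pediatric phase I data in Section 2.4.3**
- Any grade, drug-related: "40 of all 41 treated subjects (97.6%) reported at least 1 regorafenib related TEAE". 40/41 = 97.6%.
- Worst grade 3 or above, drug-related: 11 (Grade 3) + 4 (Grade 4) = 15; 15/41 = 36.6%.
- Affected subjects below Grade 3: 40 − 15 = 25, of whom 22 are given as Grade 2, leaving 25 − 22 = 3 at Grade 1.
- Largest possible undercount: 25/41 = 61.0 percentage points, or 25/40 = 62.5% of affected subjects.
- Range for the tabulated drug-related proportion: 36.6% (none of the 25 enters through an exception or voluntary entry) to 97.6% (all of them do).

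**4. Dose changes in the same data.** AE-led interruptions by dose level were 3 + 10 + 7 + 6 = 26, and 26/41 = 63.4%. Even if all 15 subjects with a drug-related Grade 3+ event were among the 26, at least 26 − 15 = 11 interruptions occurred in subjects without one. This is not a count of lost subjects, because some of the 11 may have had an unrelated Grade 3+ event or a recordable laboratory abnormality.

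**5. ECG.** It is absent from the on-study list (Section 9.2) and the off-study list (Section 9.3). Scheduled post-baseline ECGs: 0.

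**The case against.** The strongest reply is that Grade 3 is a minimum. Section 7.1.1.3 grades all adverse events from 1 to 5 and asks for detail only from Grade 3. Section 7.1.2 wants the final outcome of each event on the CRF, and Section 4.1 says safety data are captured in the eCRFs. Adverse events are evaluated at visits, diaries are collected, and the eCRFs and Operations Manual are not in the file. Secondary objective A also speaks of reported events, and no decision rule uses these variables.

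Much of this stands. A reader might infer that only Grade 3+ events are recorded and that the tables cannot be produced. The documents do not support that: the three provisions below Grade 3 are real, and sites may enter more than they must. What remains is narrower. The general statements set no rule for entering non-serious Grade 1–2 clinical events, and source data without an entry rule do not give a consistent numerator. The word *reported* does not make a mostly Grade 3+ count an all-grade one.

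It is also fair that Table 6.2 makes no dose change for most Grade 0–2 toxicities, and that reduction at a first Grade 2 hand-foot skin reaction is only to be considered. The documents therefore give no figure for how many modifications in this trial would follow Grade 2 clinical events.

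**Conclusion.** The point holds in this form. Four TAAE variables (any, drug-related, leading to dose modification, leading to discontinuation) have no grade limit, while non-serious Grade 1–2 clinical events have no explicit eCRF duty. The proportions would be undercounted or would rest on voluntary entry. The planned ECG change has no scheduled data behind it; ECGs done for clinical reasons would be a selected sample.

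On the phase I illustration the drug-related proportion could be understated by up to 61 percentage points. A reader might infer that 97.6% would simply be tabulated as 36.6%. That does not follow. The latter is a lower bound, since the leading drug-related events there included transaminase, bilirubin and blood-count abnormalities, some of which could enter through Section 7.1.3. Nor do the documents show that overall tolerability would look far better than it is: the serious, Grade 3+, laboratory and vital-sign variables are unaffected. The phase I figures illustrate the mechanism and do not forecast this trial. The primary endpoints are untouched, but the safety tables should be corrected.

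**What to change.** - **Section 7.2.1:** extend the principle of Section 7.1.3 to clinical events, so that an AE of any grade leading to dose interruption, reduction or discontinuation is entered on the eCRF. Cohorts A–C have completed enrollment, so this applies prospectively to cohorts D and E (24 patients in total).
- **Section 12.1.2:** label the any, drug-related, dose-modification and discontinuation variables by what had to be collected: Grade 3 or worse, plus SAEs and clinically significant laboratory abnormalities. This matters most for cohorts A–C. If the eCRF instructions, which are not in the file, already require all grades, say so in Section 7.2.1 and keep the all-grade labels.
- **ECG:** reconcile Section 12.1.2 with the calendar. With no scheduled post-baseline ECG, remove the change-from-baseline summary from the planned analyses.

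The cost is protocol wording, a modest amount of extra eCRF entry and less inclusive table titles. No visit, test or dosing rule changes. AEs are already evaluated at visits, and diaries (Appendix C) and dispensing records (Section 8.5) give a source for dose changes, although the protocol names no eCRF field for them.

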### 1.2. Secondary Objectives

A. All cohorts: Calculate the incidence of reported CTCAE v 4.03 adverse events and abnormal laboratory test results

B. All cohorts: Estimate the overall response rate (ORR) per RECIST version 1.1, time to tumor progression (TTP), PFS at 8 weeks and 16 weeks, overall survival (OS), disease-specific survival (DSS)

C. Cohorts A and B, after crossover: Assess PFS, RR, TTP, OS, and DSS following administration of regorafenib in the open label portion of the study.

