## **12.2 Study Design/Endpoints**

### **Cohorts A and B (liposarcoma and osteosarcoma)**

Each of cohorts A and B will be studied using a randomized placebo controlled phase II design with a progression free survival endpoint. Outcomes will be determined on an intention to treat analysis.

Each cohort substudy will be powered to detect a difference of at least 3 months in median PFS, which has been discussed among expert sarcoma oncologists as a clinically meaningful difference in outcome. This corresponds to a median control group PFS of 2 months, median treatment group PFS of 5 months, and hazard ratio of 0.4 for treatment/control groups.

42 events are needed to detect a targeted difference with 90% power and 5% one-sided significance level. The final analysis of the primary PFS endpoint will be conducted when at least 42 patients had disease worsening. 48 eligible patients are expected to be randomized, to achieve the 42 expected events with an enrollment rate of 4 eligible patients per month per substudy. With the predicted accrual rate and PFS parameters, the 42 events are expected to occur in 16 months.

We will limit to a maximum of 16 patients per substudy A & B with WHO performance status of 2. There is no such limitation for substudy C.

Survival will be estimated by the Kaplan-Meier method. The treatment groups will be compared with a one-sided stratified log rank test. All analyses will be done in the intention-to-treat population.

We will conduct a prognostic factor analysis for PFS using a univariate Cox model; significant factors subsequently will be included in a multivariable Cox regression model (cutoff  $p < 0.05$ ). For a predictive analysis of PFS, Cox models will be generated with the investigated factor, treatment, and their interaction, with a significance value of  $p < 0.05$ . P-values will not be adjusted for multiple comparisons.

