## **12.5 Analysis of Secondary Endpoints**

Descriptive statistics will be generated for secondary endpoint variables.

Methodologies for variables that are proportions will include construction of confidence intervals for each group and for the difference between groups. For example, a Fisher exact test will be used for single-population analyses, while a Mantel-Haenszel test will be used for analyses combining data across strata.

Methodologies for time-to-event variables will include construction of 95% confidence intervals for each group separately and for the difference between groups. For analysis, a log-rank test will be used. Logistic regression and analysis of covariance methods on measured variables with baseline measures as covariables. Kaplan Meier curves will be displayed for time-to-event data.

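### In Cohorts A and B, adverse events are contrasted between arms as crude proportions although the design assumes different time on treatment, so later-onset or constant-rate events not caused by regorafenib can look more frequent on it

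*Combined protocol and SAP*

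**What the plan says.** Section 1.2 makes safety a secondary objective in all cohorts: "Calculate the incidence of reported CTCAE v 4.03 adverse events and abnormal laboratory test results". Section 12.1.2 lists the event-based variables as proportions of patients: any event, serious events, "Proportions of patients with Grade 3 or greater TAAEs", events leading to discontinuation or dose modification, drug-related events, and abnormal laboratory values.

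Section 12.5 covers secondary endpoints: "Methodologies for variables that are proportions will include construction of confidence intervals for each group and for the difference between groups". For testing, "a Fisher exact test will be used for single-population analyses", with Mantel-Haenszel across strata. It also provides Kaplan-Meier and log-rank methods for time-to-event variables, but 12.1.2 defines no adverse-event variable of that kind. Neither section sets a person-time rate, a common time window or any other adjustment for time at risk.

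Treatment continues until progression or another stopping reason (5.6). Assignment is unblinded at progression so that placebo patients can cross over (4.3). Adverse events are reported up to 30 days after the last dose (7.2.1). Section 12.1.2 derives the placebo period and the open-label regorafenib period separately. Section 12.2 gives the design assumption: "This corresponds to a median control group PFS of 2 months, median treatment group PFS of 5 months", with a "hazard ratio of 0.4 for treatment/control groups".

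**The concern.** A crude proportion combines how often an event occurs with how long patients are observed. Here the observation time is expected to differ by arm, and to differ more the better the drug works. Keeping the placebo and open-label periods separate rightly stops crossover toxicity from entering the placebo count. It also leaves placebo patients with only the short blinded period.

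The blinded placebo contrast is the trial's randomized evidence on which events come from the drug and which from the disease. If it is read from crude proportions, part of any excess on regorafenib may be longer observation. The monitoring committee (11.1.6.1) and the risk-benefit closure criterion (11.5) both draw on safety data of this kind.

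**Working it through.** **Inputs from the documents.** Median PFS 2 and 5 months, hazard ratio 0.4, 42 events, 90% power, one-sided 5%, analysis expected at 16 months (12.2); 48 patients per cohort randomized 1:1, so 24 per arm, with 12 months of accrual and at least 6 months of follow-up (12.3); 30-day reporting tail (7.2.1), taken as 1 month.

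**Assumptions.** PFS is exponential and stands in for time on treatment. The background event has a constant hazard λ, equal in both arms, of 0.05 to 0.20 per month.

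**The plan's own figure.** Schoenfeld's formula with 1:1 allocation: 4(1.645 + 1.282)² / (ln 0.4)² = 40.8, so 41 events. With 42 events power is 0.907. The stated 42 is reproduced, so the 2 and 5 month medians are the working design assumption.

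**Exposure.** Progression hazards are μ = ln 2/2 = 0.347 (placebo) and ln 2/5 = 0.139 (regorafenib) per month. Mean times are 1/μ = 2.89 and 7.21 months, ratio 2.5. With uniform 12-month accrual and a cut-off, mean exposure is 2.71 vs 5.19 months at 16 months (ratio 1.91) and 2.80 vs 5.68 at 18 months (ratio 2.03).

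**Proportion with the event.**
- Full follow-up: P = λ/(λ + μ).
- With a tail w: P = 1 − e^(−λw) μ/(λ + μ).
- With cut-off T and entry at u: put C = T − u and c = C − w. The probability of no event is e^(−λw) [μ/(λ + μ)] (1 − e^(−(λ+μ)c)) + e^(−λC) e^(−μc), averaged over u from 0 to 12. Where C ≤ w it is e^(−λC).

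Placebo vs regorafenib, with the ratio in brackets, for an event unrelated to the drug:

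| Scenario | λ = 0.05 | λ = 0.10 | λ = 0.20 |
|---|---|---|---|
| Full follow-up, no tail | 12.6% vs 26.5% (2.10) | 22.4% vs 41.9% (1.87) | 36.6% vs 59.1% (1.61) |
| 16-month cut-off, no tail | 12.1% vs 21.6% (1.79) | 21.7% vs 36.6% (1.69) | 36.0% vs 55.4% (1.54) |
| 16-month cut-off, tail in both arms | 16.1% vs 24.4% (1.52) | 28.8% vs 41.3% (1.44) | 47.2% vs 62.2% (1.32) |
| 16-month cut-off, tail on regorafenib only (immediate crossover) | 12.1% vs 24.4% (2.02) | 21.7% vs 41.3% (1.90) | 36.0% vs 62.2% (1.73) |

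**Smaller benefit.** Full follow-up, no tail, λ = 0.05, 0.10, 0.20: a regorafenib median of 4 months gives 1.78, 1.63, 1.46; a median of 3 months gives 1.41, 1.35, 1.27.

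**Testing.** A two-sided 5% Fisher test with 24 per arm, full follow-up, flags the unrelated event with probability 15%, 22% and 27% at the three hazards, against about 2 to 3% with equal exposure.

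**Checking candidate remedies.**
- *Simple 8-week proportion* (t = 56/30.4375 = 1.84 months): P = [λ/(λ + μ)] (1 − e^(−(λ+μ)t)). At λ = 0.10 this is 12.5% vs 14.9%, ratio 1.19, so the artefact shrinks but remains.
- *Exposure-adjusted rate.* The expected ratio is 1.0 for a constant-hazard unrelated event. Now take an illustrative event confined to month 1, hazard 0.20 on regorafenib and 0.10 on placebo. Crude proportions are [0.20/0.339](1 − e^(−0.339)) = 17.0% and [0.10/0.447](1 − e^(−0.447)) = 8.1%. Mean time at risk to first event or end of treatment is 0.85 + 5.14 = 5.99 and 0.81 + 1.85 = 2.65 months. The rates are 0.0283 and 0.0304 per month, ratio 0.93: a real doubling disappears.
- *Censoring-adjusted cumulative incidence at 8 weeks.* The unrelated event at λ = 0.10 gives 1 − e^(−0.184) = 16.8% in both arms. The month-1 event gives 1 − e^(−0.20) = 18.1% vs 1 − e^(−0.10) = 9.5%, ratio 1.9. It passes both checks when censoring is non-informative.

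**The case against.** The strongest reply is that the between-arm comparison has to be inferred. The objective is to calculate incidence, 12.5 opens with descriptive statistics, its sentence on proportions is generic and also serves response rate and landmark PFS, and no decision rule rests on an adverse-event test. That is fair. Even so, adverse-event incidence is a listed secondary objective measured by proportions, so 12.5 applies as written and nothing exempts it.

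There is also partial protection. Drug-related events are tabulated, causality is assessed by an investigator who is blinded until progression (4.3, 7.1.1.4), and clear progression is not reported as an adverse event (7.1.1.6). So the placebo contrast is not the only safeguard. Crude proportions are also a valid description of what patients experience when treated to progression. Both points stand, but neither equalizes time at risk in the contrast.

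A reader might infer that regorafenib patients will be exposed 2.5 times as long and that unrelated events will generally look twice as frequent. The documents do not support that. The 2.5 is a ratio of assumed PFS medians under the alternative. Treatment also stops for other reasons (5.6, section 6), a 16- to 18-month cut-off brings mean exposure to about 1.9 to 2.0-fold, and the 30-day tail in both arms lowers the event ratio further. Nor does the plan overstate toxicity whenever the drug works: that needs an equal background hazard and events that are not confined to the first weeks.

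**Conclusion.** The point holds for the blinded comparison in Cohorts A and B. Cohorts C, D and E have no control arm. As written, the plan contrasts proportions over unequal time at risk with no adjustment. If PFS is prolonged as assumed, constant-rate or later-onset events that the drug does not cause will look more frequent on regorafenib.

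The size depends on a background hazard that the documents do not give. For 0.05 to 0.20 per month the ratio is about 1.6 to 2.1 with full follow-up, 1.5 to 1.8 at 16 months, and 1.3 to 1.5 at 16 months with the tail in both arms. At 0.10 per month the absolute excess runs from 19.5 points (full follow-up) down to 12.5 points (cut-off and tail). Immediate crossover raises the ratio; a smaller PFS benefit or stopping for toxicity lowers it; early drug effects are little affected. The primary PFS analysis is untouched. This is a worthwhile, inexpensive correction to the safety analysis.

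**What to change.** In 12.1.2 and 12.5:

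- Keep the crude proportions as description.
- For any, serious, and Grade 3 or greater events, base the between-arm contrast on time to first event in the blinded period, using the Kaplan-Meier and log-rank methods already in 12.5.
- Censor at the end of the blinded at-risk window, defined as the first open-label dose or 30 days after the last blinded dose, whichever comes first. Treat death as a competing event, so that cumulative incidence (Aalen-Johansen) replaces one minus Kaplan-Meier where deaths occur.
- Report cumulative incidence at 8 weeks by arm, with the difference and its confidence interval.
- Add exposure-adjusted incidence with a rate ratio and confidence interval as a supplement only, noting that it assumes a constant hazard and dilutes front-loaded toxicity.
- Reconcile 10.1.1, which starts toxicity evaluability at first regorafenib, with 12.1.2, which counts placebo patients from first placebo dose.

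The cost is a few table lines. The analysis assumes that censoring at progression is non-informative, which is open to question for events linked to worsening disease and should be stated. The sponsor must also confirm that onset dates are in the eCRF, since 7.2.1 limits when the specific time of onset is needed. Enrollment to A and B is complete (3.1.4), so no visits or patients are added.
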